4.6.4. Clinical Trial Registry Analyses

Additional analyses will be performed for the purpose of fulfilling the Clinical Trial Registry (CTR) requirements.

Analyses provided for the CTR requirements include the following:

Summary of adverse events, provided as a dataset which will be converted to an XML file. Both Serious Adverse Events and ‘Other’ Adverse Events are summarized: by treatment group, by MedDRA preferred term.

- An adverse event is considered ‘Serious’ whether or not it is a treatment emergent adverse event (TEAE).
- An adverse event is considered in the ‘Other’ category if it is both a TEAE and is not serious. For each Serious AE and ‘Other’ AE, for each term and treatment group, the following are provided:
 - the number of participants at risk of an event
 - the number of participants who experienced each event term
 - the number of events experienced.
- Consistent with www.ClinicalTrials.gov requirements, ‘Other’ AEs that occur in fewer than 5% of participants/subjects in every treatment group may not be included if a 5% threshold is chosen (5% is the minimum threshold).
- AE reporting is consistent with other document disclosures for example, the CSR, manuscripts, and so forth.

4.7. Safety Analyses

4.7.1. Extent of Exposure

Days of exposure will be calculated for each participant (date of last dose – date of first dose + 28). Additionally, days in study will also be calculated for each participant (end date of study participation – date of first dose). Summary statistics will be provided for the total number of days and participant-years of exposure by treatment.

The number and percentages of participants that stopped dosing due to meeting centiloid stopping criteria will be reported for donanemab participants at the time points associated with the post-baseline florbetapir F18 PET scans.

4.7.2. Adverse Events

Treatment-emergent adverse events (TEAEs) will be defined as events that first occurred or worsened after the randomization date (Visit 2 date). Should there be insufficient data for AE start date, stop date, and time to make this comparison, the AE will be considered treatment-emergent. The MedDRA lower-level term (LLT) will be used in the treatment-emergent computation. The maximum severity for each lower-level term (LLT) during the baseline period will be used as baseline.

An overview of AEs, including the number and percentage of participants who died, suffered serious adverse events (SAEs), discontinued due to AEs and who suffered TEAEs, will be provided. Comparison between treatments will be performed using Fisher’s Exact Test.

Summaries of AEs by decreasing frequency of PT within SOC will be provided for the following:

- Preexisting conditions
- TEAEs
- TEAEs by maximum severity
- TEAEs occurring in greater than or equal to 2% of participants by PT
- Serious adverse events
- Adverse events reported as reason for study treatment discontinuation

These summaries will include number and percentages of participants with TEAEs. Treatment comparisons will be carried out using Fisher's Exact Test.

Hypersensitivity and Infusion-Related Reactions (IRR) will be summarized and compared between treatment groups using Fisher's Exact test. Hypersensitivity and IRR will be broken out between Potential Immediate (defined as TEAEs occurring on the date of infusions) and Potential Non-Immediate (defined as TEAEs not occurring on the date of infusions but prior to the administration of a subsequent infusion). The following will be used to identify such TEAEs:

- Anaphylactic reaction SMQ (20000021; narrow, algorithm per SMQ guide, and broad)
- Hypersensitivity SMQ (20000214; narrow and broad)
- Angioedema SMQ (20000024; narrow and broad)
- Event maps to Preferred Term (PT) of Infusion related reaction (10051792)

The number and percentage of participants who experienced a TEAE for the following will be analyzed:

- Any narrow or algorithmic term from any one of the 3 SMQs indicated above (that is, combined search across narrow and algorithmic portions of all 3 SMQs)
- Any narrow scope term within each SMQ, separately (that is, narrow SMQ search)
- Any term within each SMQ, separately (that is, broad SMQ search)

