Day Relative to Randomization	Can be done any time prior to complete screening	-49 to -1	
Tolerance Interval for Visit (Days)	Can be done at any time	≤49 before V2	
Screening PET Scans and MRI			
Florbetapir F18 PET scan		X	The participant should meet all other non-imaging eligibility criteria before the screening florbetapir F18 PET scan. Previous florbetapir F18 PET scans within 3 months of randomization may be acceptable. The acceptance of a historical scan is at the discretion of the sponsor.
MRI		X	The participant should meet all other non-imaging eligibility criteria before the screening MRI.

Abbreviations: ApoE = apolipoprotein E; CDR = Clinical Dementia Rating; C-SSRS = Columbia-Suicide Severity Rating Scale; ECG = electrocardiogram; IWRS = interactive web response system; MMSE = Mini-Mental State Exam; MRI = magnetic resonance imaging; PET = positron emission tomography; V = visit.

Visits 2 through 11

	Open-Label Study Period										Comments
Visit Number	2	3	4	5	6	7	8	9	10	11	
Weeks relative to first infusion	0	4	8	12	16	20	24	28	32	36	
Visit interval tolerance (days)		-7 to +10	±7	±7	±7	±7	±7	±7	±7	±7	
Entry and Administrative											
Inclusion and exclusion criteria, review and confirm	X										Inclusion and exclusion criteria should be confirmed at V2, prior to randomization and administration of the first dose of study intervention.
Randomization	X										
Brief Physical/Neurological Exam	X			X			X			X	As described in the Manual of Operations. Any clinically significant changes from baseline on brief physical/neurological examinations should be noted on the AE CRF.
Concomitant medications	X	X	X	X	X	X	X	X	X	X	
AEs	X	X	X	X	X	X	X	X	X	X	Any events that occur after signing the informed consent are considered AEs as defined in Section 10.3.
C-SSRS screening/baseline	X										
C-SSRS since last assessment			X		X		X		X		
Administer study intervention	X	X	X	X	X	X	X	X	X	X	See Section 6.1. Administration of study intervention (and treatment-related activities conducted in person) outside of the visit window is not a protocol deviation, unless 2 doses are administered within <21 days of each other. The participant should be observed for a minimum of 30 minutes following the end of each infusion.

	Open-Label Study Period										Comments
Visit Number	2	3	4	5	6	7	8	9	10	11	
Weeks relative to first infusion	0	4	8	12	16	20	24	28	32	36	
Visit interval tolerance (days)		-7 to +10	±7	±7	±7	±7	±7	±7	±7	±7	

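### The TEAE definition starts after the Visit 2 date, so non-serious reactions on the first-infusion day are left out of the TEAE, immediate-reaction and registry 'Other' counts

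*SAP*

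**What the plan says.** SAP 4.7.2 counts as treatment-emergent "events that first occurred or worsened after the randomization date (Visit 2 date"). It adds a default for incomplete records: "Should there be insufficient data for AE start date, stop date, and time to make this comparison, the AE will be considered treatment-emergent". Severity before treatment is handled by a further rule: "The maximum severity for each lower-level term (LLT) during the baseline period will be used as baseline". The section does not define that period.

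Two safety summaries depend on TEAE status:

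- Hypersensitivity and infusion-related reactions are split by timing, and the first group is "Potential Immediate (defined as TEAEs occurring on the date of infusions"). The arms are compared with Fisher's exact test.
- In SAP 4.6.4, a registry event goes in the 'Other' "category if it is both a TEAE and is not serious". Registry serious events are counted whatever their TEAE status.

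In the protocol (section 1.3), the Visits 2 through 11 table marks both randomization and study drug administration at Visit 2. Visit 2 is Week 0 on a row labelled "Weeks relative to first infusion". The comment on eligibility reads: "Inclusion and exclusion criteria should be confirmed at V2, prior to randomization and administration of the first dose of study intervention".

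SAP 4.8.2, on concomitant therapy, instead dates randomization to the day before the first dose. Protocol 9.3.2.3, which defines the same medication categories, equates randomization with Visit 2.

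**The concern.** The TEAE clock starts strictly after a calendar date on which, by the schedule, the first infusion is given. The definition therefore excludes a day on which participants are already exposed and on which an immediate infusion reaction can occur. The omission carries into the one category meant for infusion-day reactions, because that category is built from TEAEs.

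This matters because hypersensitivity, both immediate and non-immediate and including infusion reactions, is a named special-interest topic in protocol 8.3.4. The protocol commits to analyzing it as the SAP sets out. The trial is open label with about 100 participants per arm, so a few participants can change a displayed rate. The TEAE anchor is also out of line with the rest of the SAP: baseline (4.1) and exposure (4.7.1) are both tied to the first dose.

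**Working it through.** The point concerns a definition. The plan has no figure that depends on it, so there is none to reproduce. The check is date logic, followed by an illustration of size.

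**Date logic.** Let R be the randomization date, D the first-infusion date and A the AE onset date, all complete. The SAP rule is: TEAE if A > R. The alternative is: TEAE if A ≥ D, with clock times compared when A = D.

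| Anchor | Onset relative to first infusion | SAP rule | First-infusion rule |
|---|---|---|---|
| Protocol schedule, R = D | same day | not a TEAE | TEAE if onset follows infusion start |
| Protocol schedule, R = D | 1 day later | TEAE | TEAE |
| Protocol schedule, R = D | 28 days later | TEAE | TEAE |
| SAP 4.8.2, R = D − 1 day | same day | TEAE | TEAE if onset follows infusion start |
| SAP 4.8.2, R = D − 1 day | 1 or 28 days later | TEAE | TEAE |

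Only the first row loses events. Under the SAP 4.8.2 dating nothing is lost, but an event with onset on D before the infusion starts is called treatment-emergent although the participant has not been exposed.

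**What a lost event misses.** A non-serious first-day reaction is absent from the TEAE tables, from the immediate-reaction group and from registry 'Other'. A serious one also misses the TEAE and immediate-reaction counts, but appears in the SAE summary and in registry 'Serious'. An event that starts that day and worsens later can still qualify.

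**Baseline severity.** If the undefined baseline period includes the Visit 2 date, a first-day reaction becomes the baseline for its lower-level term. A later event under the same term of equal or lower severity would then not count either. If the pre-first-dose baseline of SAP 4.1 applies, this second loss does not arise.

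**Illustrative size.** About 200 participants randomized 1:1 gives n = 100 per arm. Let r be the proportion whose only qualifying event is a non-serious reaction on the first-infusion day. The documents do not give r, so it is assumed. Expected loss is n × r, with a 95% binomial range; the chance of losing at least one is 1 − (1 − r)^100.

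| Assumed r | Expected loss per arm | 95% range | Chance of at least one |
|---|---|---|---|
| 1% | 1 | 0–3 | 63% |
| 2% | 2 | 0–5 | 87% |
| 5% | 5 | 1–10 | 99% |
| 10% | 10 | 5–16 | >99% |

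**Effect on a comparison (assumed counts).** Two-sided Fisher's exact test, 100 per arm: 8 vs 1 gives p = 0.035. With one case lost from the larger arm, 7 vs 1 gives p = 0.065. With two lost, 6 vs 1 gives p = 0.118.

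**Effect on display thresholds.** One participant moves 5/100 to 4/100, below the registry's 5% cut. The term can be omitted only if that cut is chosen and the term is below 5% in every arm. For the table of "TEAEs occurring in greater than or equal to 2% of participants by PT", 2/100 to 1/100 falls below the cut if it is applied per arm, though the term remains in the full TEAE table.

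**The case against.** The strongest reply is that the SAP can be read consistently. The schedule puts both procedures at Visit 2 but does not say that they share a calendar date. SAP 4.8.2 is the SAP's only statement of the gap and puts randomization a day earlier. If Visit 2 starts the day before dosing, every first-infusion-day event is after the anchor. The week labels were changed from randomization to first infusion in protocol amendment a, which suggests that the two dates can differ. In addition, the incomplete-data sentence mentions time, which a date-only comparison would not need, so same-day events may be meant to be resolved by clock time.

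Part of this stands. A participant infused on a date later than the anchor loses nothing, and the SAP author may have intended a time comparison. It does not remove the problem. The SAP 4.8.2 dating sits in the concomitant-therapy section and fits poorly with a schedule that makes Visit 2 Week 0 from the first infusion. The time sentence applies only when data are insufficient: a complete onset date equal to the Visit 2 date can be compared with a date, and no anchor time is given.

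The objections to magnitude are fair. The rates are assumed, and a participant who reacts again at a later infusion is still counted, subject to the severity rule. The Fisher example was chosen near 0.05: of the 210 count pairs with a larger arm of 1 to 20 per 100 and a smaller count in the other, removing one case from the larger arm crosses 0.05 in only 10. From 10 vs 1, losing two leaves 8 vs 1 and p = 0.035. The rule also applies to both arms, and safety tests are outside the multiplicity scheme. The listed hypersensitivity endpoint concerns serious reactions, which are captured elsewhere.

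**Conclusion.** The concern holds. For any participant infused on the Visit 2 date, the rule as written drops fully dated, non-serious first-infusion-day reactions from three outputs. This is a stated rule that gives a wrong count, not a missing detail, and the SAP's other dating of randomization leaves the outcome to the programmer's choice. The logic needs no assumption beyond the schedule's pairing of randomization and first infusion on one date. The size does rest on assumption: about 1 to 10 participants per arm if the day-1-only rate is 1% to 10%. The effect is confined to the reporting of non-serious events, with serious events losing only their place in the TEAE and immediate-reaction counts. It should be fixed before the safety tables are programmed.

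**What to change.** In SAP 4.7.2, define a TEAE as an event that first occurs or worsens on or after the date and time of the first infusion. On that date, compare onset time with infusion start time, and treat the event as treatment-emergent if the onset time is missing. State that the baseline period ends when the first infusion starts. Reconcile the dating of randomization in SAP 4.8.2 with protocol 9.3.2.3 and the Schedule of Activities.

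The cost is SAP and programming wording. A few Visit 2 events that began before the infusion but have no recorded time may be counted as treatment-emergent. That errs toward over-reporting and is in keeping with the SAP's own default for incomplete data.

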4.1. Overall Design

Study AACN is a multicenter, randomized, open-label, head-to-head, Phase 3 study of donanemab compared to aducanumab in participants with early symptomatic AD.

Participants who meet entry criteria will be randomized in a 1:1 ratio to 1 of the following treatment groups:

- donanemab: 700 mg IV Q4W for first 3 doses and then 1400 mg IV Q4W
- aducanumab: refer to PI/routine clinical practice

The maximum total duration of study participation for each participant, including screening and the post-treatment follow-up periods, is up to 127 weeks:

- Lead-In: any time prior to complete screening
- Complete Screening: up to 7 weeks
- Open-label study period: 76 weeks
- Follow-Up: up to 44 weeks

The maximum duration of treatment is 72 weeks.

Scheduled Reduction of Donanemab

Participants randomized to donanemab whose amyloid plaque reduction as measured by florbetapir F18 PET scans at Visit 8 (Week 24) or Visit 15 (Week 52) meets criteria will stop donanemab infusions but continue all other assessments for the remaining duration of the open-label period and short-term follow-up period. These dose reduction rules are defined by the sponsor.

Participants randomized to aducanumab will continue monthly infusions throughout the open-label period, regardless of amyloid plaque reduction on florbetapir F18 PET scans.

Change in amyloid burden (as assessed with florbetapir F18 PET by personnel blinded to treatment allocation) will be compared in donanemab and aducanumab-treated participants.

Participant randomization will be stratified by amyloid burden and ApoE ϵ 4 status (noncarrier/heterozygous/homozygous).

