4.1. General Considerations

Statistical analysis of this study will be the responsibility of the Sponsor or its designee.

Unless otherwise noted, tests of treatment effects will be conducted at a 2-sided alpha level of 0.05 (or equivalently, a 1-sided 0.025 alpha level); 2-sided CIs will be displayed with a 95% confidence level. If relevant, tests of interactions between treatment and other factors will be conducted at an alpha level of 0.05.

Participant assignment to treatment will be stratified by ApoE ϵ 4 genotype, and baseline amyloid level. These factors will be included in analysis models unless otherwise stated.

All amyloid plaque analyses will follow the ITT principle unless otherwise specified. An ITT analysis is an analysis of data by the groups to which participants are assigned by random allocation, even if the participant does not take the assigned treatment, does not receive the correct treatment, or otherwise does not follow the protocol.

When change from baseline is assessed, participants will be included in the analysis only if both a baseline and a postbaseline measure are available. Unless otherwise defined, a baseline measure is the last non-missing observation collected prior to the first administration of study medications. Endpoint is the last non-missing post-baseline measurement.

To allow for sequential testing, database locks and the testing of corresponding primary and key secondary objectives are expected to occur after all randomized participants have had a chance to complete the scheduled 24-week PET scan, the scheduled 52-week PET scan, and the scheduled 76-week PET scan. If an interim analysis occurs, a database lock will additionally occur after a sufficient number of participants (for example, approximately 75-125) have had a chance to complete the scheduled 24-week PET scan. Data collected during the immunogenicity and safety follow-up period will be summarized and analyzed separately.

Any change to the data analysis methods described in the protocol will require a protocol amendment only if it changes a principal feature of the protocol. Any other change to the data analysis methods described in the protocol, and the justification for making the change, will be described in the SAP and the clinical study report. Additional exploratory analyses of the data will be conducted as deemed appropriate.

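### Same-day infusion reactions and AE-related treatment discontinuation are compared only as crude percentages, although donanemab infusions stop by PET rule and aducanumab infusions do not

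*SAP*

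**What the plan says.** **Dosing.** Protocol 4.1 has a donanemab participant whose Week 24 or Week 52 PET "meets criteria will stop donanemab infusions but continue all other assessments for the remaining duration of the open-label period" and short-term follow-up. For the comparator, "Participants randomized to aducanumab will continue monthly infusions throughout the open-label period, regardless of amyloid plaque reduction on florbetapir F18 PET scans".

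**Safety comparison.** SAP 4.7.2 states that "Hypersensitivity and Infusion-Related Reactions (IRR) will be summarized and compared between treatment groups using" Fisher's exact test, and for the listed search terms that "The number and percentage of participants who experienced a TEAE for the following will be analyzed". The same section lists "Adverse events reported as reason for study treatment discontinuation" among the summaries reported as counts and percentages and compared with Fisher's test. Hypersensitivity and infusion reactions are split into Potential Immediate events (on an infusion date) and Potential Non-Immediate events (on another date, but before a subsequent infusion). Treatment-emergent status begins at randomization and has no end tied to the last dose.

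**Exposure.** SAP 4.7.1 summarizes exposure days and participant-years by arm, and the number of donanemab participants who "stopped dosing due to meeting centiloid stopping criteria". SAP 4.8.1 summarizes the number of complete infusions by arm. All of this is descriptive. Neither document uses infusions or treatment time as a denominator for these events, or plans a time-to-event analysis or a common exposure window for them.

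**The concern.** A participant whose infusions have stopped cannot have a reaction on an infusion date and has no study treatment left to discontinue for an adverse event. That participant nevertheless stays under assessment and in the denominator. The difference in opportunity is planned, affects one arm only, and depends on the efficacy outcome.

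Safety and tolerability versus aducanumab is a stated secondary objective that names serious hypersensitivity reactions. Protocol 8.3.4 makes hypersensitivity, including infusion reactions, a topic of special interest for the study report. If the percentages and p-values stand alone, a reader cannot tell how far a difference, or its absence, reflects the drug and how far the number of infusions.

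**Working it through.** **The plan's own figure.** The documents give no figure for this safety comparison. The clearance rates borrowed below come from the sample-size sections, which claim at least 98% power for 35.7% versus 3.0% at 6 months. At two-sided 0.05, a two-proportion calculation gives over 99.9% with 90 per arm and 98.5% with 45 per arm, so that claim is reproduced.

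**Inputs from the documents**
- One infusion every 4 weeks from Week 0, with a 72-week maximum: 7 infusions through Week 24, 14 through Week 52 and 19 through Week 72.
- Planned donanemab clearance: 35.7% at 6 months and 50.1% at 12 months.

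**Assumptions**
- The sponsor-defined stopping criteria are not given. Clearance stands in for stopping: 35.7% after Week 24, a further 50.1 − 35.7 = 14.4% after Week 52, and 49.9% never.
- The per-infusion risk q is the same in both arms and constant. The documents give no value, so 0.5%, 1% and 2% are tried.
- No dropout.

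**Expected infusions.** Donanemab: 0.357×7 + 0.144×14 + 0.499×19 = 2.50 + 2.02 + 9.48 = 14.0. Aducanumab: 19. The ratio is 0.74, or 26% fewer.

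Sensitivity:
- 20% stopping at Week 24 and 35% by Week 52: 0.20×7 + 0.15×14 + 0.65×19 = 15.85, 17% fewer.
- 50% and 70%: 0.50×7 + 0.20×14 + 0.30×19 = 12.0, 37% fewer.
- Stop one infusion earlier (6 and 13) or later (8 and 15): ratio 0.71 or 0.76.
- The schedule of activities marks study intervention at Visit 21 (Week 76), against the 72-week maximum in Protocol 4.1; these passages must be reconciled. With 20 infusions the ratio is 14.5/20 = 0.73.

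**Crude percentage at equal risk.** For k infusions the chance of at least one event is 1 − (1 − q)^k. At q = 1% this is 6.8%, 13.1% and 17.4% for k = 7, 14 and 19. Donanemab: 0.357×6.8 + 0.144×13.1 + 0.499×17.4 = 13.0%.

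| q per infusion | Donanemab | Aducanumab | Ratio | Fisher p≤0.05 favouring donanemab, 100 per arm |
|---|---|---|---|---|
| 0.5% | 6.7% | 9.1% | 0.74 | 5% |
| 1% | 13.0% | 17.4% | 0.75 | 10% |
| 2% | 24.2% | 31.9% | 0.76 | 18% |

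Fisher's test favours aducanumab in 0.3% of trials or fewer. At q = 1%, the figures through Week 52 are 10.9% versus 13.1%. Through Week 24 planned infusions are equal and there is no gap.

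**If risk falls after infusion 7** (1% for the first seven, r×1% afterwards):

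| r | Donanemab | Aducanumab | Ratio |
|---|---|---|---|
| 50% | 10.0% | 12.2% | 0.82 |
| 25% | 8.4% | 9.6% | 0.88 |
| 10% | 7.4% | 7.9% | 0.94 |
| 0 | 6.8% | 6.8% | 1.00 |

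**Rate per infusion.** Counting infusions up to and including the first event, expected infusions at risk are [1 − (1 − q)^k]/q, so first events per infusion at risk equal q for any k. Both arms give 0.50, 1.00 and 2.00 per 100 infusions at the three values of q.

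**Treatment time.** SAP 4.7.1 defines exposure as last dose minus first dose plus 28 days. In weeks, 0.357×28 + 0.144×56 + 0.499×76 = 56.0 versus 76, again a ratio of 0.74. Days in study do not shorten at a rule-based stop and would not correct anything.

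**Potential Non-Immediate events.** Their window closes at the next infusion; after a final infusion there is none. SAP 4.1 says "Data collected during the immunogenicity and safety follow-up period will be summarized and analyzed separately", which at most closes the window at Week 76. That is 76 − 24 = 52 weeks after a last infusion at Week 24, but 4 weeks after one at Week 72. This can add donanemab events.

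**The case against.** The strongest reply is that the PET-based stop belongs to the assigned donanemab regimen. Fewer infusions causing fewer reactions is a real consequence of that regimen, and the randomized percentages estimate it validly. This stands: a reader might infer that the Fisher comparison is biased or should be withdrawn, but it answers a question about regimens and should stay. What it cannot do alone is separate drug risk from infusion count.

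Second, the direction is not settled for the whole hypersensitivity row. It includes Potential Non-Immediate events found by broad searches, and their open-ended window may count against donanemab. This also stands, so the directional statement covers only Potential Immediate reactions and AE-related discontinuation.

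Third, the size is assumed: stopping shares are a proxy, no per-infusion risk is given, and constant risk is doubtful because Protocol 7.1 and 8.3.3.2 remove participants with suspected anaphylaxis from further dosing. This limits the size. Under equal risk at every infusion number, the gap vanishes only if risk after the early infusions is nil.

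Fourth, infusion totals (SAP 4.8.1) and event counts by term (SAP 4.6.4) are already planned, so a rough events-per-infusion figure could be assembled. But no rate, ratio or interval is specified, and registry counts by preferred term are not limited to same-day events.

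Finally, safety is outside the multiplicity scheme and no stated study decision depends on these p-values. That makes this an inexpensive improvement to interpretation, not a threat to the trial's main conclusions.

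**Conclusion.** The point holds for Potential Immediate reactions and AE-related treatment discontinuation. The planned percentages compare the regimens validly but cannot be read as a difference in drug tolerability, and nothing planned beside them supplies that reading.

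With clearance as the proxy for stopping, donanemab participants are expected to receive about 26% fewer infusions (17% to 37% over the range tried). At constant equal risk the crude ratio is about 0.75; it is 0.94 to 1.00 if risk after infusion 7 is 10% of its early level or nil. No separate size can be given for AE-related discontinuation, because the documents give no discontinuation risk; the same formula applies with q read as that risk.

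A reader might infer that donanemab will look safer across all hypersensitivity outcomes. The documents do not support that, because the Potential Non-Immediate window can work the other way. Nor do they support making an early-window test the main comparison: a cut after the Visit 8 infusion would leave out 12 of the 19 planned infusions.

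**What to change.** Keep the Fisher table in SAP 4.7.2, labelled as a comparison of regimens as assigned. Then:

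1. For Potential Immediate reactions and AE-related treatment discontinuation, add first events per 100 infusions given and per participant-year on treatment, each with a rate ratio and 95% confidence interval. Count infusions and time up to the first event. Base treatment time on the exposure definition in SAP 4.7.1, not on days in study.
2. Add a supplementary between-arm comparison of events before the first infusion the PET rule could withhold. State which infusion that is: the schedule puts both the PET scan and an infusion at Visit 8 without giving their order.
3. Give the Potential Non-Immediate window a fixed end after the last infusion, the same in both arms.

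The cost is SAP wording and a few tables from dosing and AE dates already collected. The early-window comparison has fewer events and is less precise, which is why it should stay supplementary.
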